An effect of Cohen's $d = 0.27$ has been observed for a digital intervention for BPD that is based on ST only (27). Given that *alivis* consists of a combination of DBT, ST, ACT, and MSC and that participants will be closely guided during the trial, we expect the observed effect to be slightly larger and assume an effect size of $d = 0.30$. In order to obtain a power of 0.80, at a two-sided significance level of 0.05, each group should have a sample size of 176. Outpatient RCTs for BPD have an average dropout rate of approximately 25% (28,29). To compensate for dropouts, we thus aim to include and randomize $N = 470$ (2×235) participants with an allocation ratio of 1:1.

d) Primary and secondary hypotheses

~~The primary hypothesis is that receiving *alivis* in addition to TAU leads to a better reduction of BPD symptoms measured with BSL-23 at T1 (three months after the start of the intervention), compared to receiving TAU only. Secondary hypotheses are (i) intervention group participants will exhibit a better reduction of depressive symptoms at T1, compared to those in the control group; (ii) a better reduction of anxiety symptoms, (iii) reduced costs caused due to the participant's BPD, (iv) higher social and work-related functioning, (v) greater mental health-related quality of life, (vi) fewer BPD symptoms (regarding all 9 BPD criteria) measured with the Borderline Personality Disorder Checklist (BPD-CL), and (vii) higher patient activation compared to those in the control group at three months.~~

~~In addition, exploratory moderator analyses will be used to determine whether certain baseline variables have an influence on the effectiveness of *alivis*. The following variables will be recorded a priori: currently attending psychotherapy, currently taking psychotropic medication, childhood trauma, and BPD symptom severity.~~

Let the mean treatment difference be defined as μ (= *alivis* + TAU minus TAU only).

For the primary endpoint, the following two-sided hypothesis is planned to be tested.

- BPD symptoms (BSL-23) at T1
 - H0: $\mu = 0$ points against HA: $\mu \neq 0$ points

For the confirmatory secondary endpoints, the following confirmatory one-sided hypotheses are planned to be tested.

- Depressive symptoms (PHQ-9) at T1
 - H0: $\mu = 0$ points against HA: $\mu \neq 0$ points
- Anxiety symptoms (GAD-7) at T1
 - H0: $\mu = 0$ points against HA: $\mu \neq 0$ points
- Costs (self-compiled cost questionnaire) at T1

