~~The GAD-7 is a self-administered patient questionnaire used as a screening tool and severity measure for generalized anxiety disorder (GAD) (37). Studies report good reliability, as well as criterion, construct, factorial, and procedural validity (38,39).~~

Costs caused due to the patient's BPD

Costs caused due to BPD will be assessed with a self-compiled instrument assessing inpatient and outpatient treatment, support from friends, family and professional services, contacts with members of the judicial authorities and public security, medication, sick leave, and physician/therapist visits during work time.

Social Functioning at T1, assessed via the Work and Social Adjustment Scale (WSAS).

The WSAS is a 5-item self-report scale to measure social functioning in regard to physical, mental and social health as well as age group referenced competence for performance. The PROM has good psychometric properties with good criterion validity, good sensitivity and strong internal consistency ($\alpha = 0.89$) (40). Individual items address work, home management, social leisure, private leisure and relationships. Each item is rated on a 9-point Likert scale from 0 = “not at all impaired” to 8 = “very severely impaired”. The total score has a range of 0-40, with lower scores denoting less disability.

~~The WSAS is a scale to measure social functioning in regard to physical, mental, and social health as well as age group referenced competence for performance. The PROM is validated for a representative German sample (40).~~

Health-Related Quality of Life at T1, assessed via the AQoL-8D score on the Assessment of Quality of Life-8 Dimensions (AQoL-8D), German version

The AQoL-8D is a health-related quality-of-life questionnaire consisting of 35 items forming eight health dimensions:

independent living, happiness, mental health, coping, relationships, self worth, pain, senses. Validation of the AQoL-8D assessing health-related quality of life showed good psychometric properties in a German patient sample, including excellent reliability (Cronbach's $\alpha = 0.96$) and construct validity (strong correlation with the SF-36, $r = .81$) (41).

~~The AQoL-8D is a self-administered questionnaire to measure quality of life in 8 dimensions (independent living, happiness, mental health, coping, relationships, self worth, pain, senses) which has demonstrated good psychometric properties in a German sample (41).~~

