6.5 Monitoring plan

Documented monitoring visits will be conducted before, during (twice) and after the trial (close-out visit) by the sponsor to ensure adherence to the study protocol. The following items will be monitored during the audits: (i) presence of approval by ethical review board, (ii) qualification of investigators, (iii) current status of recruitment and participant flow, (iv) adherence to study protocol (e.g., presence of informed consent, correct application of inclusion and exclusion criteria, allocation to correct intervention, usage of intervention) and (v) correctness of data entries and consistency with the source documents.

7. Statistical design and analysis

All analyses and imputation procedures will be performed using standard statistical software such as *R* (59) or *SPSS*.

a) Analysis population

In line with recommendations of the CONSORT eHealth statement, we will conduct both intention-to-treat (ITT) and per-protocol (PP) analyses (60–62). For PP-analyses, the dataset will be filtered based on the variable “usage time”. Individuals in the intervention group who did not use *alivis* for at least 4 times on 4 different days will be excluded from the PP dataset. Additionally, we will exclude participants from both groups who reported using other digital health interventions for BPD for the relevant follow-up period.

b) Descriptive statistics of baseline data, treatments, safety data

Descriptive statistics will include mean value and standard deviation (or median, min, max and quartiles as appropriate) for continuous data and absolute numbers and percentages for categorical data. These will be presented separately for the intervention and control group at baseline.

c) Analytical procedures and measures of precision

The Principal Investigator will receive access to all data prior to analysis and will remain blinded to group assignment until the end of the analysis of the primary outcome and main safety outcome (suicide attempts).

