Analysis of effectiveness of the intervention in addition to TAU vs. TAU will be performed by ANCOVA of the primary endpoint and all secondary endpoints (tested in sequential order in a gatekeeping testing strategy, see section 7. k), in which the posttreatment scores at T1 will be compared between treatment groups (intervention group vs. control group), using the baseline scores of the respective outcome as a covariate. Treatment effects, i.e., the difference in posttreatment scores, will be reported on the original scale, along with the 95%-CI. In addition, Cohen's *d* (calculated as between-group difference divided by the pooled standard deviation) will be used as a standardized effect size to quantify differences in posttreatment outcomes. Tests of prolonged treatment effects at T2 and T3 will be performed analogously with baseline as covariate. The ITT analyses will comprise all randomized participants, with imputed outcome values as described in section 7. m.

Analysis of binary or count outcomes (such as medication or number of hospitalizations) will be conducted based on non-responder imputed data in the form of χ^2 -tests and Poisson regression, as appropriate, to examine between-group effects at T1, and analogously for T2 and T3.

The primary analysis will be performed as an ITT analysis with multiple imputation under ‘missing at random’ (MAR) assumption. In addition, a conservative sensitivity analysis based on reference-based multiple imputation (J2R imputation) will be calculated (63).

An exploratory PP analysis will be conducted (61,62). For PP analyses, the dataset will be filtered based on the variable “usage time”. Individuals in the intervention group who did not use *alivis* for at least 4 times on 4 different days will be excluded

from the PP dataset (62). Additionally, we will exclude participants from both groups who reported using other digital health interventions (e.g., DiGAs, apps, online programs) for BPD for the relevant follow-up period.

Measures of accuracy will be p -value [significance level (α) < 0.05] and the corresponding 95% confidence interval.

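### The stated blinding lapses before the six confirmatory secondary endpoints and does not cover the analysts, while the euro valuation of costs, third in the test sequence, is still open

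*Combined protocol and SAP*

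**What the plan says.** **Blinding.** Section 7.c states: "The Principal Investigator will receive access to all data prior to analysis". It adds that this person "will remain blinded to group assignment until the end of the analysis of the primary outcome and main safety outcome (suicide attempts"). No other section extends the blind to another endpoint. Section 6.4.b lists data analysis among the activities of sponsor representatives, with no blinding stated for them. Section 16.b treats rules for breaking the code as not applicable.

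**Status of the secondary endpoints.** Section 5.d introduces them with: "For the confirmatory secondary endpoints, the following confirmatory one-sided hypotheses are planned to be tested". There are six, all at T1: PHQ-9, GAD-7, costs, WSAS, AQoL-8D and PAM-13. Section 7.c has them "tested in sequential order in a gatekeeping testing strategy". Section 7.k leaves the two-sided 5% level unadjusted for that reason and takes the order from 6.1.c. Section 5.d equates this with a one-sided overall level of 2.5%.

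**Outcome definitions.** The costs hypothesis in 5.d is in euros. Section 6.1.c says: "Costs caused due to BPD will be assessed with a self-compiled instrument" and then names resource categories, including informal support, contacts with judicial authorities, sick leave, and medical visits in working time. It gives no unit prices, no rule for valuing unpaid help or lost work, no perspective and no aggregation rule. Quality of life is "assessed via the AQoL-8D score"; 6.1.c gives the number of items and the dimensions but prints no formula or range. The other four have stated score ranges in 6.1.c.

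**The concern.** The plan makes confirmatory claims on seven efficacy endpoints and guarantees blinding for one. The endpoint it covers, BSL-23, is a mean item score with little left to decide. Costs have the most left to decide, and they come after the guarantee has run out.

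The position of costs adds weight. In a fixed sequence, a significant costs result opens the tests of WSAS, AQoL-8D and PAM-13. A valuation settled after by-arm results are known could therefore bear on four of the six confirmatory secondary claims. The people doing the analysis represent the sponsor, and nothing in the plan keeps them from knowing the arms at any stage.

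**Working it through.** **1. Coverage of the blind against the confirmatory family**

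| Order | T1 endpoint | Covered by 7.c guarantee | Outcome variable fixed in 6.1.c |
|---|---|---|---|
| Primary | BSL-23 | yes | yes, mean score 0–4 |
| 1 | PHQ-9 | no | yes, 0–27 |
| 2 | GAD-7 | no | yes, 0–21 |
| 3 | Costs | no | no, resource categories only |
| 4 | WSAS | no | yes, 0–40 |
| 5 | AQoL-8D | no | one named score, formula not printed |
| 6 | PAM-13 | no | yes, 13–52 |

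Six confirmatory endpoints lie outside the guarantee. One of them has no rule that turns the answers into the tested quantity.

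**2. The plan's own level**

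Two-sided 5% means a critical value of 1.96, and P(Z > 1.96) = 0.025 in the favourable direction. This agrees with 5.d and holds when there is one valuation, fixed in advance.

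**3. Effect of choosing among valuations after seeing results**

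Assumptions, not figures from the documents: k defensible valuations, test statistics standard normal with no true effect on costs, all pairs correlated at rho. The most favourable version is kept. With φ and Φ the standard normal density and distribution function, the favourable-direction error is

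1 − ∫ φ(u) · [Φ((1.96 − √rho · u) / √(1 − rho))]^k du.

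| k | rho | Favourable-direction error |
|---|---|---|
| 1 | – | 2.5% |
| 2 | 0.9 | 3.5% |
| 2 | 0.7 | 4.2% |
| 4 | 0.9 | 4.7% |
| 4 | 0.7 | 6.5% |

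**4. Does blinding remove this?**

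Take an analyst who sees only arms A and B, tests two-sided, and keeps the valuation with the largest |z|. The chance that at least one |z| exceeds 1.96 is 7.0%, 8.3%, 9.4% and 13.0% for the same four rows. By symmetry half of these errors favour alivis: 3.5%, 4.2%, 4.7% and 6.5%. The figures equal those in step 3. The inflation comes from the open valuation combined with sight of a by-arm result, not from knowing which arm is which.

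**5. When the figures apply**

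Costs are tested only after BSL-23, PHQ-9 and GAD-7 have all been significant. If none of those three has a true effect, costs are reached in the favourable direction at most 2.5% of the time, because BSL-23 alone must first pass at that level. The rates in step 3 are therefore conditional on the first three tests having passed, with no true effect on costs.

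**The case against.** The strongest reply is that the plan already closes most of the freedom. Section 7.c fixes ANCOVA, the baseline covariate and the T1 comparison for every endpoint; 6.1.c and 7.k fix the order; 7.m fixes the imputation method and its variables; and 7.o requires deviations to be disclosed in the register, report and publication. Blinding the investigator through the primary and main safety outcomes can be read as a deliberate scope. All of this stands and limits the risk, but none of it defines the euro amount that enters the costs ANCOVA.

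A reader might infer more than the documents support, in four respects:

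- **That the investigator is unblinded before the secondary analyses.** Section 7.c says how long blinding is guaranteed. It describes no act of unblinding and does not time one against the secondary ANCOVAs. Only the lapse of the guarantee is shown.
- **That the early end of the blind causes the error inflation.** Step 4 of the working shows that it does not.
- **That the investigator would choose the scoring.** The documents do not say who does. Analysis belongs to sponsor representatives, so extending the investigator's blind alone would miss them.
- **That AQoL-8D can be steered in the same way as costs.** Section 6.1.c names one score on a published instrument with a cited source. The documents show only that the formula is not printed.

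**Conclusion.** The concern holds in limited form. The blinding stated in 7.c does not reach any of the six confirmatory secondary endpoints, and none is stated for the analysts. The practical exposure is at costs, where the plan gives no valuation rule, and through costs at the three endpoints behind it. AQoL-8D is a lesser documentation gap.

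The illustrative size is a favourable-direction error of about 3.5%–6.5% instead of 2.5% at the costs test. It rests on assumed k of 2 to 4 and rho of 0.7 to 0.9, on selection after results are seen, and on BSL-23, PHQ-9 and GAD-7 having passed. A reader might go on to conclude that the overall one-sided 2.5% level is lost in general. The sequence does not support that without these conditions, and the primary test is not affected. The change is still worth making: it is a specific protection at almost no cost, and it brings an existing rule into line with the endpoints the plan calls confirmatory.

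**What to change.** 1. In 7.c, state that the principal investigator and everyone who carries out the data analysis stay blinded to group assignment until the T1 analyses of the primary endpoint, all six confirmatory secondary endpoints and the main safety outcome are complete.
2. Fix and date the euro valuation of the cost items (unit prices, treatment of unpaid help and lost work, perspective, aggregation) before any by-arm T1 result is seen, including results with coded arms. Name the AQoL-8D scoring algorithm in the same document.

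The second item removes the inflation shown in the working. The first protects whatever discretion remains. Sample size, significance level and visits do not change. The cost is slightly later unblinding, since all six ANCOVAs use the same T1 data, and an earlier decision on cost valuation.

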~~Severity of borderline symptoms at T1, assessed via the Borderline Personality Disorder Checklist (BPD-CL).~~

~~The BPD-CL is a DSM-IV based self-report instrument to assess BPD symptoms in the previous month (42). Importantly, in contrast to the BSL-23, the BPD-CL explicitly assesses all nine DSM-5 criteria.~~

Patient activation at T1, assessed via the Patient Activation Measure (PAM-13)

The PAM13 assesses patients' active participation in their medical care using 13 items (43,44). Items are answered using a Likert scale ranging from 1 = "strongly disagree" to 4 = "agree strongly", yielding a total score between 13 and 52. The German version of the PAM13, the PAM13-G, is validated and demonstrates good psychometric properties, including a good internal consistency of Cronbach's $\alpha = 0.84$ (44). An improvement of 4 points on the PAM-13 is considered an MCID (56). Therefore, responders will be defined as patients who improve by at least 4 points on the PAM-13 from T0 to T2. The proportion of responders between groups will be compared using χ^2 tests.

~~The PAM-13 is a 13-item instrument assessing patients' active participation in their medical care (43). The German version of the PAM-13, the PAM-13-G, is validated and demonstrates good psychometric properties (44).~~

Exploratory Endpoints: Assessments listed in "Secondary endpoints" at T2/T3

Sociodemographic Variables:

- Age
- Gender

- Sex
- Education
- Employment Status
- Family Situation
- Language ability
- Ethnicity

Clinical Variables:

Assessed at T0 only:

- First diagnosis (date)
- Inclusion diagnosis (BPD) using the respective section of the SCID-5-PD interview (45)
- Psychiatric comorbidities (via Mini-DIPS) (46)
- Psychotherapy (past, type)

Assessed at all timepoints (T0-T3):

- Medications (name of medication, dose, frequency)
- Psychotherapy (current, type)
- Childhood trauma (via Childhood Trauma Questionnaire (CTQ; 47,48))
- Number of BPD-related hospitalizations (T0: past 12 months, T1-T2: past 3 months, T3: past 6 months)
- Number of hospitalizations due to other reasons (T0: past 12 months, T1-T2: past 3 months, T3: past 6 months)
- Number of days in sick leave (past 3 months)
- Number of days in sick pay (past 3 months)
- weight and height (current)
- Use of any other online program for BPD (T0: lifetime, T1-T2: past 3 months, T3: past 6 months; name)

Treatment satisfaction:

- Program Evaluation of the Program (NPS, Net Promoter Score) (49)

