The outcome of the study may be influenced by a number of confounding factors (e.g., age, gender, therapy, etc.). Randomization of participants to the intervention or control group ensures approximately equal distribution in both groups, so that any differences between groups can be attributed to the intervention. Potential differences in baseline values in the outcome variables of interest will be controlled for by including them as covariates in analyses of covariance (ANCOVA).

d) Methods for addressing these factors

See section 6.4 c.

e) Follow-up period for clinical performance, effectiveness or safety

The follow-up periods of three months (primary timepoint for assessment of effectiveness), six months and 12 months (for stability of effects) have been shown to be valid and relevant periods for treatment of BPD-patients with unguided internet-based self-management interventions (25,27).

f) Specific medical care provided following the clinical investigation

Not applicable. Participants have access to routine care by the attending health care professionals over the course of the study.

g) Recommended follow-up for the subjects

Not applicable.

h) Final disposition or potential future use of samples obtained from subjects

Not applicable.

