Moreover, responder analyses will be conducted. Unless a specific MCID is specified for an endpoint in section 6.1d), responders will be defined by reaching the cut-off of 15% of the range of the scale (64). ~~the reliable change index (RCI; 33) will be used to identify responders to treatment in patients with complete observations. The RCI is calculated as the ratio of the difference between pre- and post-scores of an individual participant (numerator) and the standard error of measurement of the difference (denominator). RCI scores larger than 1.96 indicate that it is unlikely that the posttest score is not reflecting real change ($p < .05$), thus indicating that the participant is a responder (33).~~ If a specific MCID is specified for an endpoint, responder analyses will instead be based on that value. Responders will then be defined as participants reaching this difference from T0 to T1. Additionally, exploratory responder analyses will be conducted for each endpoint, where response is defined as 50% improvement since baseline. The proportion of responders between groups will be compared using χ^2 tests. Moreover, the odds ratio will be reported.

d) Significance level and power

significance level (α) = 0.05 (two-sided)
power = 0.80

e) Sample size

1) Clinical data on outcome variable and effect size

An effect of Cohen's $d = 0.27$ has been observed for a digital intervention for BPD that is based on ST only (27). Given that *alivis* consists of a combination of DBT, ST, ACT, and MSC and that participants will be closely guided during the trial, we expect the observed effect to be slightly larger and assume an effect size of $d = 0.30$. In order to obtain a power of 0.80, at a two-sided significance level of 0.05, each group should have a sample size of 176. Outpatient RCTs for BPD have an average dropout rate of approximately 25% (28,29). To compensate for dropouts, we thus aim to include and randomize $N = 470$ (2×235) participants with an allocation ratio of 1:1.

2) Expected outcomes across treatment groups

See 5. d.

3) Adjustments due to pre-planned interim analyses

An interim analysis is planned after three months (T1; primary time point). There will be no adjustments.

4) Effect size and non-inferiority margin

See 7. e 1).

5) Randomization allocation ratio

1:1, in variable blocks of 4, 8, or 16 participants each ~~no block randomization, no stratification~~

6) Expected drop-out rate

25% (28,29).

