f) Procedures to be performed by user and analysis

Not applicable.

g) Pass/fail criteria

Not applicable.

h) Interim analysis and criteria for termination

Dataset will be open for interim analysis after the last patient completed T1. Results of the interim analysis will have no consequences for further study conduct.

i) Management of bias

Accompanying clinical variables of the participants are recorded at baseline, post-treatment (T1) and follow-up (T2, T3). It is conceivable that differences in e.g., the concomitant therapy in both groups in the course of the study could influence the study result. The observation period is chosen so that both the intended and unexpected effects of the program can be assessed with validity.

j) Management of potential confounding factors

The result of the study could be influenced by a number of confounders (e.g., age, gender, therapy, etc.). By randomizing the participants to the intervention or control group, roughly equal distribution in both groups can be assured, so that possible differences between groups can be attributed to the intervention. Additionally, potential differences in baseline values in the outcome variables of interest will be controlled for by including them as covariates in ANCOVA.

k) Multiplicity control and adjustment of error probabilities

No adjustment of the significance level α of 0.05 (two-sided) given that a gatekeeping testing strategy will be applied as suggested by the FDA (65). The secondary endpoints (listed in section 6.1.c) are listed in priority order for that approach.

l) Subgroups for analysis

The following subgroup analyses are planned:

- a) effectiveness of *alivis* depending on sex (male, female, intersex);
- b) effectiveness of *alivis* depending on gender (male, female, diverse);
- c) effectiveness of *alivis* in patients with concomitant psychotherapy at baseline compared to those without;
- d) Effectiveness of *alivis* in patients who take psychotropic medication (ATC codes N05, N06) at baseline compared to those who do not;
- e) Effectiveness of *alivis* in patients with changes in treatment (i.e., psychotherapy or regular psychotropic medication) between baseline and T1 vs. patients without changes in treatment;
- f) Effectiveness of *alivis* in patients with previous diagnosis of BPD vs. in patients who were initially diagnosed with BPD as part of the study.

Results of these subgroup analyses will be visualized as a table and forest plot.

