m) Missing, unused or spurious data, including drop-outs

In the ITT analysis, missing data points will be imputed using the respective variable values at baseline as well as group membership and other sociodemographic and clinical variables (~~such as~~ age, sex, education, employment, family status, psychotherapy at baseline, psychotherapy ever). The ITT analysis will be implemented following a computationally efficient implementation for bootstrapped maximum likelihood multiple imputation (67,68) by von Hippel and Bartlett (2021) using the *R* packages *bootImpute* (68) and *mice* (69). In detail, 1,000 bootstrap samples of the incomplete dataset will be generated for each outcome variable and then the relevant outcome variable will be imputed twice with the *mice* package with default settings (i.e., using predictive mean matching with a pool of 5 candidate values) as recommended.

n) Exploratory analysis and sensitivity analysis

Exploratory moderator analyses will determine the influence of certain baseline variables on the effectiveness of *alivis*. The following variables will be established a priori: currently attending psychotherapy, BPD symptoms (BSL-23), and patient activation (PAM-13).

Reference-based sensitivity analysis ('jump to reference' (63,68,70)) will be applied following procedures for the ITT-analysis, using an implementation for the *R* programming environment. Assumptions about the structure of missing data points will be tested in advance.

o) Reporting of deviation(s) from original statistical analysis plan

If there are deviations from the original statistical planning, this deviation will be stated in the study register, study report and the publication as well.

p) Handling potential imbalance of numbers of subjects across investigation sites

Not applicable.

q) Strategy for pooling data

Not applicable.

r) Estimand strategy

The treatment policy estimand will be used to handle any potential intercurrent events. In this study, intercurrent events are defined as the initiation or discontinuation of psychotherapeutic or psychotropic treatment and the discontinuation of *alivis* usage for any reason in the intervention group. The treatment policy estimand evaluates the treatment effect for all randomized patients, irrespective of their use of *alivis* or specific elements of TAU.

The following estimand strategy attributes are defined:

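### Optional improvement, not an error: the 7.c ANCOVAs adjust only for the outcome's own T0 score, and pre-specifying a few baseline covariates could add a little precision

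*Combined protocol and SAP*

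**What the plan says.** Section 7.c compares T1 scores between arms by ANCOVA for the primary endpoint and, in gatekeeping order, the secondary endpoints, "using the baseline scores of the respective outcome as a covariate". Later visits follow the same model: "Tests of prolonged treatment effects at T2 and T3 will be performed analogously with baseline as covariate".

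On other prognostic factors, 6.4.c states that "The outcome of the study may be influenced by a number of confounding factors (e.g., age, gender, therapy, etc"., and 7.j that "The result of the study could be influenced by a number of confounders (e.g., age, gender, therapy, etc".). Both sections answer with randomisation plus one adjustment. In 7.j this reads: "potential differences in baseline values in the outcome variables of interest will be controlled for by including them as covariates in ANCOVA".

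The variables themselves are available and used elsewhere:
- Section 6.1.c records age, sex and gender, and also medication and current psychotherapy from T0 onwards.
- Section 7.m imputes missing outcomes from the outcome's baseline value, group and "age, sex, education, employment, family status, psychotherapy at baseline, psychotherapy ever". Psychotropic medication is not on that list.
- Section 7.l plans subgroup analyses by sex (three categories), gender, psychotherapy at baseline and psychotropic medication at baseline. Section 7.n makes current psychotherapy a moderator.
- Section 7.e.5 describes allocation as "1:1, in variable blocks of 4, 8, or 16 participants each", with no stratification factor.

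**The concern.** The plan names three possible influences on the outcome, and neither the allocation scheme nor the confirmatory model deals with any of them directly. Randomisation balances them on average, but one trial can still be unlucky. TAU ranges from psychotherapy and medication to no treatment at all (6.2.a), so baseline therapy is a plausible prognostic factor. For a factor present in half the participants, with 176 per arm, the 95% range of chance imbalance is ±1.96 × √(2 × 0.25/176) = ±0.10. If that factor shifted the T1 score by 0.3 SD given the T0 score (an assumption), an imbalance at the edge of that range would move the estimate by 0.10 × 0.3 = 0.03 SD, a tenth of the assumed d = 0.30.

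In a linear model, adjusting for baseline covariates leaves the estimand in 7.r, a mean difference, unchanged. What is at stake is the width of the confidence interval for the primary endpoint. The same applies to the six secondary endpoints, where one failed test in the sequence closes all later ones.

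**Working it through.** **The plan's own figure.** Inputs from 7.d and 7.e: d = 0.30, two-sided α = 0.05, power 0.80, dropout 25%. An unadjusted two-sample t-test needs 175.4, so 176 per arm, and 176/0.75 = 234.7, so 235 per arm and N = 470. The stated size reproduces. It takes no credit for any covariate, not even the T0 score.

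**Assumptions.** The documents give neither the correlation r between T0 and T1 scores nor the R² added by further covariates. The BSL-23 test-retest reliability of .82 in 6.1.c is at best an upper guide to a three-month correlation. I take r = 0.5 as the central value, with 0.4 and 0.6 as alternatives, and an added R² (ΔR²) of 2, 5 and 10% of total variance.

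**Formula.** With total variance 1 and k extra covariate terms, on 352 evaluable participants:

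residual variance v = (1 − r² − ΔR²) × 348/(348 − k)

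The last factor approximates the price of estimating k more coefficients. For k = 4 it is 348/344 = 1.0116. For the T0-only model it is 1. Power is that of a t-test with effect d/√v and 176 per arm. The gain in evaluable participants is 352 × (1 − r²)/v − 352.

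**Results for r = 0.5, k = 4** (T0-only variance 0.75):

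| ΔR² | v | Cut in residual variance | Equivalent participants (of 352) | Power, d = 0.30 | Power, d = 0.27 |
|---|---|---|---|---|---|
| T0 score only | 0.750 | – | – | 0.900 | 0.831 |
| 2% | 0.73 × 1.0116 = 0.738 | 1.5% | 5.5 | 0.904 | 0.836 |
| 5% | 0.70 × 1.0116 = 0.708 | 5.6% | 20.8 | 0.916 | 0.851 |
| 10% | 0.65 × 1.0116 = 0.658 | 12.3% | 49.5 | 0.933 | 0.876 |

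The d = 0.27 column uses the effect that 7.e.1 cites from the earlier digital intervention.

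**Other values of r, d = 0.30.** At r = 0.4, power goes from 0.865 to 0.869 / 0.881 / 0.900. At r = 0.6 it goes from 0.939 to 0.943 / 0.953 / 0.967.

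**Break-even.** Let p be the partial R² given the T0 score. The gain is zero when (1 − p) × 348/(348 − k) = 1, so p = k/348. That is 4/348 = 0.0115 for four terms and 5/348 = 0.0144 for five, the count if sex enters with all three categories in 7.l. With ΔR² = 0.5% at r = 0.5, v = 0.745 × 1.0116 = 0.754, slightly worse than 0.750.

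These figures treat 176 per arm as complete cases. They do not model what multiple imputation recovers from the participants with missing T1 data.

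**The case against.** The strongest reply is that nothing here is defective. The planned model is valid and its covariate is pre-specified. The T0 score is likely to be the best single predictor, and the sample size does not rely even on that. At r = 0.5, power is already 0.90 against a target of 0.80. Entry also requires treatment stable for at least 30 days and no plan to change it for three months (6.3), so the T0 score may already carry much of the therapy information. All of this stands.

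Three stronger readings are tempting, and the documents support none of them:
- A reader might infer that the plan declares age, gender and therapy prognostic and then contradicts itself by omitting them. Sections 6.4.c and 7.j say only that they *may* or *could* matter. They treat the issue as confounding and answer it with randomisation.
- A reader might infer that chance imbalance invalidates the estimate or its standard error. It does not: the standard error already allows for such imbalance.
- A reader might infer that precision is being given away at no cost. No R² is stated, and weak covariates yield nothing or a very small loss.

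Nor is it inconsistent to use a variable in imputation and not in the analysis model. Auxiliary variables there support the missing-at-random assumption and need not all be covariates. What remains is that the variables are at hand, are baseline measures and are considered relevant elsewhere in the plan, so a short pre-specified list is a reasonable and inexpensive choice.

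**Conclusion.** This is a worthwhile option of small and uncertain size. The confirmatory analysis is valid as written and adequately powered on its own assumptions. Over r = 0.4 to 0.6 and an added R² of 2 to 10%, four extra baseline covariates would raise power at d = 0.30 by about 0.4 to 3.6 percentage points. The 10% case has no support in the documents and should be read as an upper illustration. The conclusion rests on assumed values of r and R², on a linear model with baseline covariates only, and on 352 evaluable participants. If the covariates explain less than about 1.1% of the variance left after the T0 score, nothing is gained.

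**What to change.** - **Section 7.c.** For the continuous primary and secondary ANCOVAs, pre-specify these covariates in addition to the respective T0 score: age, sex, psychotherapy at T0 (yes/no) and psychotropic medication at T0 (yes/no). State a rule for a sparse third sex category. Use baseline values only, because starting or stopping therapy later is an intercurrent event under 7.r. Say whether T2 and T3 use the same set.
- **Section 7.m.** Add psychotropic medication at T0 to the imputation model, and to the jump-to-reference analysis that follows the same procedure. Otherwise outcomes would be imputed without a covariate that the analysis model uses.
- **Timing.** Fix the list before the T1 data are opened for analysis. Sections 6.1.d and 7.h open them after the last T1 assessment, well before the full data set is available after T3, so a deadline tied to final database lock would be too late.
- **Reporting.** Give the model with the T0 score alone as supportive.

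The cost is four or five degrees of freedom, a short addition to 7.c and a small edit to 7.m. No new data collection is needed.
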